14.2 Study population definitions

All main analyses will be according the intention to treat principle i.e. patients will be analyzed according to the treatment arm they were assigned to, regardless of whether they received any of the study treatment or not. However, patients initially registered and/or randomized but considered

ineligible afterwards based on information that should have been available before registration and/or randomization, whichever applicable, will be excluded from the respective analyses.

14.3 Alerting rules

Criteria to generate a safety report for discussion of the safety results with PI and DSMB are:

- An unacceptable profile or incidence rate of AE/ AEsI revealed in this or any other study in which at least one of the investigational products of this trial is administered
- Any serious adverse events or adverse events of special interest occurring with 20% or higher frequency at any time point during the study
- Significant number of cases of death associated with the study treatment

14.4 Statistical analysis

14.4.1 Efficacy analysis

The PFS primary endpoint will be analyzed as soon as all randomized patients have achieved the landmark of 12 months after randomization. Thus, final analysis will take place as soon as the last patient starting treatment has reached the time point month 27 and data have been assembled from all study sites. Giving an estimated 3 years recruitment period, time point of final PFS analysis is projected 5 years and 6 months after trial initiation.

The primary efficacy endpoint is the investigator-assessed proportion of patients with PFS at month 27 in arm B, the ITT population for arm B is used for calculation of the proportion. PFS is defined as all patients free of progression or relapse (determined using standard IWCLL guidelines [2008], appendix A), or death from any cause, whichever occurs first. Patients in the observation arm becoming MRD positive thus restarting treatment are still considered progression free, as long as they don't progress according to IWCLL criteria after start reinitiation treatment. If patients in the observation arm have clinical progression but achieve response within three months of reinitiating treatment, they are still considered progression free. For patients reinitiating therapy before 27 months according to the rules outlined above who have progressed according to IWCLL criteria before reinitiating treatment are allowed up to 3 months after reinitiating therapy to obtain response. These patients will be considered progression free at month 27 if a response is achieved within 3 months from reinitiating therapy.

The primary objective of the study is to test the following hypothesis:

The progression free survival rate at 12 months after randomization for the observation arm (B) is more than 60% (i.e., H_0 : PFS rate at 12 months post-randomization \leq 60% versus H_1 : PFS rate at 12 months post-randomization $>$ 60%). PFS and the 95% confidence interval (CI) will be estimated using Kaplan-Meier survival methodology, and a Kaplan-Meier survival curve will be generated to

provide a visual illustration of PFS for patients in the different treatment arms separately (from randomization), and also for all patients together (from registration).

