Study objectives	
The primary objective:
 
- Evaluate efficacy of ibrutinib + venetoclax (VI) in terms of proportion of patients fulfilling the criteria for progression free survival (PFS) at 12 months after stopping therapy (27 months after starting treatment) for patients randomized to stop treatment (arm B of the study), reinitiated treatment due to MRD positivity not considered progression (see section 13.1 for details). 
Secondary objectives (for all treatment groups):
 
- Evaluation of the efficacy in terms of minimal residual disease (MRD) at 12 months after stopping treatment (month 27),- Evaluation of efficacy in terms of PFS (IWCLL criteria),- Time to next CLL treatment,- MRD after cycle 12 (PB), at day 15 of cycle 15 (PB and BM) and at later time points in PB,- Overall Survival (OS),- Complete response (CR)/ Partial Response (PR)/ Stable disease (SD) after cycle 3, 9, 12, 15, and at month 27 and month 51 (3 years after stopping treatment),- Duration of response,- To evaluate safety with regards to type, frequency, and severity of adverse events (AEs) and adverse events of special interest (AESI) and their relationship to study

treatment,

- To evaluate patient related outcomes, measured in terms of health-related quality of life (QoL) by EORTC QLQ-C30 and QLQ-CLL16 questionnaires.

Secondary objectives (Arm B group)

- Time to and number of patients reinitiating treatment,
- Time to treatment failure after reinitiated treatment.

Study design

Phase-II trial, prospective, multicenter, open-label, randomized.

Patient population

Fit (CIRS \leq 6) and unfit (CIRS $>$ 6) patients with a creatinine clearance \geq 30 ml/min with previously treated CLL with or without TP53 aberrations requiring treatment.

Intervention

All patients receive ibrutinib + venetoclax (with delayed start and ramp up of venetoclax from cycle 3) for the 15 cycles. Patients not achieving MRD negativity after cycle 12 (PB) AND/OR day 15 cycle 15 (PB+BM) continue on ibrutinib maintenance (non-randomized group). Patients achieving MRD negativity after cycle 12 (PB) AND day 15 cycle 15 (PB+BM) are randomized 1:2 between ibrutinib maintenance (arm A) and stopping treatment (observation, arm B).

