9.3 Ibrutinib maintenance treatment

After 15 cycles of ibrutinib/venetoclax patients will be divided into three groups.

- Patients not reaching MRD negativity continue ibrutinib treatment until toxicity or progression (non-randomized patients)

Patients achieving MRD negativity after cycle 12 (PB) and at day 15 of cycle 15 (PB and BM), are randomized 1:2 between:

- Continuous ibrutinib treatment until toxicity or progression (**Arm A**)
- Treatment free observation. (**Arm B**)

Maintenance treatment (**NOT** for patients in arm B)

Agent	Dose/day	Route of administration	Cycle	Days
Ibrutinib	420 mg	Orally	1-until progression	1-28

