9.4 Reinitiation of therapy for patients randomized to arm B

Patients randomized to Arm B will get reinitiation of therapy during the observation period in case of:

- progression according to IWCLL criteria or
- $MRD \geq 10^{-3}$ (PB) and at least one month later $MRD \geq 10^{-2}$ (PB).

Treatment reinitiation will be as follows:

Venetoclax ramp up as outlined below for cycle 1, day 1 until day 28 after reinitiation, thereafter 400 mg daily (4 tablets. at 100 mg) until 12 cycles of 28 days (from reinitiation of ibrutinib).

Ibrutinib will be administered as a daily oral dosage of 420 mg (3 x 140mg) starting on day 1 of cycle 1 until:

- 1.) Progressive disease (patients not reaching any response (CR/PR/SD) according to IWCLL criteria as assessed by the local investigator after 3 cycles of reinitiated therapy are considered as progressive disease and will go off protocol treatment)

or

- 2.) unacceptable toxicity, whatever occurs first

The continuous daily administration with a slow dose escalation of venetoclax starts on cycle 1 day 1.

Agent	Dose/day	Route of administration	Cycle	Days
Ibrutinib	420 mg	Orally	1-until progression	1-28
Venetoclax	20 mg	Orally	1	1-7
Venetoclax	50 mg	Orally	1	8-14
Venetoclax	100 mg	Orally	1	15-21
Venetoclax	200 mg	Orally	1	22-28
Venetoclax	400 mg	Orally	2-12	1-28

The same precautions regarding TLS are to be taken as described in section 9.2.1.

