13.1 Primary endpoint

(Only considered for arm B of the study)

- ◆ Proportion of patients fulfilling the criteria for progression free survival (PFS) at 12 months after stopping therapy (27 months after starting treatment) for patients randomized to stop treatment. In this trial, reinitiated treatment due to MRD positivity will not be considered as progression, and symptomatic CLL according to IWCLL criteria within 12 months after randomization followed by reinitiation treatment resulting in a response (at least SD) before or at 12 months after randomization will neither be considered as progression.

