13.2 Secondary endpoints

Secondary endpoints (for all treatment groups: MRD positive non-randomized patients, patients MRD negative after cycle 12 and at day 15 of cycle 15 randomized for ibrutinib maintenance (arm A) or observation (arm B)):

- ◆ Minimal residual disease (MRD) at 12 months after stopping treatment (month 27) for patients randomized to stop of treatment.
- ◆ PFS of all study groups.
- ◆ Time to and number of patients reinitiating treatment
- ◆ Time to treatment failure after reinitiated treatment
- ◆ Time to next CLL treatment
- ◆ MRD after cycle 12 (PB), at day 15 of cycle 15 (PB and BM) and at later time points in PB
- ◆ Overall survival (OS)
- ◆ Complete response (CR)/ Partial Response (PR)/ Stable disease (SD) after cycle 3, 9, 12, 15 and month 27 and month 51 (3 years after stopping treatment)
- ◆ Duration of response
- ◆ Safety parameters: Type, frequency, and severity of
 - adverse events (AEs) and
 - adverse events of special interest (AESI) and their relationship to study treatment
- ◆ Health-related quality of life (QoL) by EORTC QLQ-C30 and QLQ-CLL16 questionnaires
- ◆ Exploratory endpoints:
 - ◆ Evaluation of relationship between various baseline markers and clinical outcome parameters
 - ◆ Various markers at time of progression
 - ◆ Correlation between MRD in BM and PB
 - ◆ Correlation between MRD in BM and PFS/OS
 - ◆ Correlation between MRD in PB and PFS/OS

14 Statistical considerations

This study is designed as a phase II study with upfront registration and a late randomization for patients who are MRD-negative at 12 and 15 cycles. The primary objective of the study is to evaluate in arm B the efficacy of ibrutinib + venetoclax (VI) in terms of PFS 12 months after stopping treatment for patients achieving MRD negativity after cycle 12 and at day 15 of cycle 15 in previously treated patients with CLL (arm B). The patients in arm A and the non-randomized patients are only considered for secondary and exploratory endpoints, and no formal comparison between randomized patients are made.

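### Section 14.4.1 gives one PFS definition with exemptions for arm B only, then plots PFS by arm and pooled, so one label covers two event rules and conflicts with the secondary IWCLL PFS

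*Protocol*

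**What the plan says.** Section 14.4.1 starts from the arm B primary endpoint, describes PFS as freedom from IWCLL progression, relapse or death, and adds exemptions. The first concerns MRD: "Patients in the observation arm becoming MRD positive thus restarting treatment are still considered progression free", provided that no IWCLL progression follows the restart. The second concerns clinical progression: "If patients in the observation arm have clinical progression but achieve response within three months of reinitiating treatment, they are still considered progression free". Section 13.1 places the same idea under the primary endpoint, which is for arm B only. There the forgiven event is "symptomatic CLL according to IWCLL criteria within 12 months after randomization followed by reinitiation treatment resulting in a response (at least SD"), with the response reached no later than 12 months after randomization.

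The restart belongs to arm B alone. Section 9.4 begins: "Patients randomized to Arm B will get reinitiation of therapy during the observation period in case of", and names IWCLL progression or a confirmed MRD rise. For arm A, section 9.3 gives "Continuous ibrutinib treatment until toxicity or progression".

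Section 14.4.1 then calls for a Kaplan-Meier estimate with a 95% CI and a curve to "provide a visual illustration of PFS for patients in the different treatment arms separately (from randomization"), plus a curve for all patients from registration. No other PFS definition comes in between. Section 14.4.3 only names PFS among the secondary analyses.

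The synopsis and section 6 list, for all treatment groups and without the exemptions, "Evaluation of efficacy in terms of PFS (IWCLL criteria"). Section 13.2 shortens this to "PFS of all study groups".

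**The concern.** Curves drawn by arm under one label are read side by side. If a first IWCLL progression counts in arm A but can be cancelled in arm B, the distance between the curves mixes any real difference with a difference in the event rule. The pooled curve from registration then combines patients under both rules.

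The protocol itself gives these curves a use. Section 14.1 states how PFS in arm A and in the MRD-positive patients is expected to compare with arm B, and section 13.2 lists correlations of MRD with PFS. Both need one event definition. As written, a statistician who follows 14.4.1 and one who follows the synopsis and section 6 would produce different arm B and pooled curves, and each could cite the protocol.

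**Working it through.** **1. The plan's own figures.** Section 14.1 has a null rate of 60%, a target rate of 75%, one-sided alpha 0.05, power 0.80, 62 patients in arm B and success at 44 or more. The exact binomial calculation gives alpha 0.0492 and power 0.812, and 62/44 is the smallest design that meets both limits. The rest of the chain also follows: 62 × 3/2 = 93; 93/0.45 = 206.7, so 207; 207/230 = 0.90. None of this depends on the point raised here.

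**2. Event rules side by side.**

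| What happens | Arm A, 14.4.1 read literally | Arm B, 14.4.1 read literally | All groups, IWCLL PFS (synopsis, section 6) |
|---|---|---|---|
| Death | event | event | event |
| IWCLL progression, no response to restart | event (no restart exists) | event | event |
| IWCLL progression, response within three months of restart | event (no restart exists) | not an event | event |
| MRD rise and restart, no IWCLL progression | does not arise | not an event | not an event (MRD is not among the PD criteria in Appendix B) |

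The third row is where the rules part. The MRD exemption removes no IWCLL event; the clinical-progression exemption does.

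**3. Direction.** With complete follow-up, removing an event or moving it later raises the survival curve at some times and lowers it at none. The exemption therefore acts in favour of arm B or has no effect. Whether a progression counts is also decided by a response seen after it.

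**4. Size by arm.** Let p be the 12-month risk of first IWCLL progression, set equal in both arms, and r the fraction of arm B progressions that are rescued. Leaving deaths aside:

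- Arm A shows 1 − p.
- Arm B shows 1 − p(1 − r).
- Gap = p × r.

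The documents give neither p nor r, so both are assumed:

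- p = 10%, r = 50%: 0.10 × 0.50 = 5 points, or 62 × 0.05 = about 3 arm B patients.
- p = 25%, r = 90%: 0.25 × 0.90 = 22.5 points, or 62 × 0.225 = about 14 arm B patients.
- Wider ranges, p = 10 to 40% and r = 25 to 75%: 0.10 × 0.25 = 2.5 points up to 0.40 × 0.75 = 30 points.
- r = 0: no gap.

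**5. Size in the pooled curve.** Planned arm B is 62 of 207 eligible patients, and 62/207 = 0.30. Compared with a pooled curve under one rule, the lift is 0.30 × 5 = 1.5 points up to 0.30 × 22.5 = about 6.7 points.

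**The case against.** The best defence is that the protocol already keeps the two definitions apart. Section 13.1 puts the exemption under an endpoint considered only for arm B. The synopsis and section 6 attach it to the primary objective and list IWCLL PFS as a separate secondary item. In 14.4.1 the exemptions follow directly on the sentence about the arm B primary endpoint, and the wording in 13.2 may be no more than a shortening. This stands to the extent that the intention was probably IWCLL PFS for the secondary endpoint. It does not settle the curves, because 14.4.1 orders them under the PFS it has just defined and never returns to the unmodified one. This is more than detail left to a statistical analysis plan, since two parts of the protocol give different rules for PFS.

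A second defence is that no formal comparison of arms is planned, that 14.4.3 and 14.4.6 make everything but the primary analysis hypothesis-generating, and that the curve is described as an illustration. This stands and limits the consequence.

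A third is that arm B is tested for MRD every three months for two years, so some patients will restart before clinical progression. That may make the pool of forgivable progressions smaller. This stands as well, and is one more reason to treat the size as illustrative.

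**Conclusion.** The point holds as a conflict of definitions with a known direction. Read literally, 14.4.1 plots arm A and arm B under one label with different event rules, and its pooled curve mixes them, against the IWCLL PFS promised for all treatment groups. For the assumed p and r the gap by arm is 5 to 22.5 points. This rests on equal progression risk in both arms and on a rescue rate that no document supplies.

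A reader might infer more, and the documents do not support it:

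- **That the arm B curve is certain to be inflated.** The literal reading of 14.4.1 leads there, but the synopsis and section 6 point the other way, and with no rescued progression there is no lift.
- **That arm B is set against the non-randomized group in the same figure.** The by-arm curves start at randomization, and those patients have no randomization date. They enter through the pooled curve and the secondary endpoint in 13.2.
- **That the primary result is affected.** It is a single-arm test with its own stated rule. The 15 points between 60% and 75% belong to that test and are no yardstick for a gap between arms.

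**What to change.** In sections 13.2 and 14.4.1, define the secondary PFS for every group, and for the pooled curve, as time to first IWCLL progression or death, with no forgiveness for a later response to restart. Use it for the by-arm and pooled Kaplan-Meier curves.

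Keep the modified rule for the arm B primary endpoint and for the Kaplan-Meier estimate and CI that 14.4.1 attaches to it. Give it its own name, for example PFS allowing successful retreatment, and show both versions for arm B. Replacing the modified rule everywhere would remove the estimate that matches the primary hypothesis.

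State which appendix defines progression. Section 14.4.1 cites Appendix A, which holds the criteria for symptomatic CLL, while the criteria for progressive disease are in Appendix B.

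The cost is wording and one extra arm B curve. Table 10.2.1 already provides for assessment at progression, and section 9.4 requires progression to be recognised before a restart on that ground, so no new data should be needed. The downside is that the secondary arm B curve may look less favourable.

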14.1 Patient numbers and power considerations

Treatment arms will be analyzed separately, only observation arm (arm B) will be considered for the primary end point. Only patients who are MRD negative after induction (i.e. MRD negative at both cycle 12 and at day 15 of cycle 15) will be randomized 1:2 for ibrutinib until progression (arm A) versus observation arm (arm B). It is expected that 45% of the registered patients will be randomized, based on the hitherto reported MRD negativity rates for venetoclax monotherapy and combination therapy with rituximab and the reported preclinical data on synergy between venetoclax and ibrutinib. The power calculation is based on the observation arm, at least equal or even better PFS is expected for the patients randomized for ibrutinib until progression. Patients who are MRD positive continuing on maintenance ibrutinib are expected to have a lower PFS than MRD negative patients.

The observation arm B is considered valuable if the PFS at 12 months after randomization is at least 75%. A success rate of less than 60% is considered not valuable for further investigation (in Phase III setting); this assumption is based on a 1-year PFS of 60% for RR CLL patients treated with FCR for the PFS endpoint (Fornecker, Am J Hem, 2015). No interim analysis on the primary endpoint is planned. An A'Hern one-stage design is used for the sample size calculation.

- Let P_0 be the largest success rate which, if true, implies that the therapeutic activity is too low and therefore does not warrant further investigation,. In the present trial, P_0 has been taken as 60%.
- Let P_1 be the smallest success rate which, if true, implies that the therapeutic activity is sufficiently high and therefore warrants further investigation in clinical trials. In the present trial, P_1 has been taken as 75%.

In order to reject the null hypothesis $H_0: P = P_0$ in favor of the alternative hypothesis $H_1: P = P_1$ with power $1 - \beta = 0.80$ (1-sided significance level $\alpha = 0.05$), 62 (eligible) patients are required in maintenance treatment arm with observation until progression (and at least 44 patients progression free at 12 months after randomization).

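### The section 14.4.1 rescue rule after clinical progression has no guard against a second progression, so a patient who progresses again before month 27 could be scored as a success

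*Protocol*

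**What the plan says.** Section 13.1 sets the primary endpoint for arm B "at 12 months after stopping therapy (27 months after starting treatment) for patients randomized to stop treatment". It excuses a symptomatic episode that is "followed by reinitiation treatment resulting in a response (at least SD) before or at 12 months after randomization will neither be considered as progression".

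Section 14.4.1 first gives the general definition, in which progression, relapse and death all count: "or death from any cause, whichever occurs first". It then deals with the two routes to restarted treatment.

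- **Restart for MRD positivity:** the patient remains progression free "as long as they don't progress according to IWCLL criteria after start reinitiation treatment".
- **Restart after clinical progression:** "If patients in the observation arm have clinical progression but achieve response within three months of reinitiating treatment, they are still considered progression free". The paragraph ends by fixing the status at the landmark for this group: "These patients will be considered progression free at month 27 if a response is achieved within 3 months from reinitiating therapy".

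Section 14.1 uses an A'Hern one-stage design with P0 = 60%, P1 = 75%, one-sided alpha 0.05 and power 0.80. It needs 62 eligible patients in arm B and at least 44 successes.

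**The concern.** The rule for clinical progression assigns the month 27 status from one earlier fact, a response within three months of restart. It does not say only that the first progression is set aside. Nothing in the two sentences withdraws the status if the patient progresses again before the landmark. The authors wrote that safeguard for the MRD group a few lines earlier, so its absence here can be read as a deliberately different rule.

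Such patients are foreseen: section 11.1 lists progressive disease after at least three cycles of reinitiated treatment as a reason for withdrawal. On the literal reading, a patient withdrawn for progression could still be counted as free of it.

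Two analysts could therefore score the same patient differently on the only confirmatory endpoint, in an open-label trial with investigator assessment. The literal reading can only add successes.

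**Working it through.** **1. The rules applied to example patients.** Times are months after randomization, so the landmark is month 12 (month 27 of the trial).

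| Record | Course | 14.4.1 restart sentence, literal | General PFS definition with the 13.1 waiver |
|---|---|---|---|
| A | Clinical progression and restart at 2, SD at 5, IWCLL progression at 8 | Success: response came 5 − 2 = 3 months after restart | Failure: the waiver covers the episode at 2, not the one at 8 |
| B | As A up to SD at 5, then death at 10 | Sentence is silent on death | Failure: death is a named event |
| C | MRD restart at 2, IWCLL progression at 8 | Failure: the guard applies | Failure |

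A and C fail in the same way after restart, yet the literal restart sentences score them oppositely. The patient with two progressions is the success. Record A is the firm case. In record B the general definition, in the same paragraph, already supplies the answer.

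**2. The plan's own design reproduced.** Inputs from section 14.1: n = 62, threshold 44, P0 = 0.60, P1 = 0.75. With X binomial(62, p):

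- P(X ≥ 44 | p = 0.60) = 0.0492
- P(X ≥ 44 | p = 0.75) = 0.8121

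A search over n from 40 to 79 gives (62, 44) as the smallest design with alpha at most 0.05 and power at least 0.80. The stated figures are right, and this point does not change them.

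**3. Effect on the threshold.** If k patients like record A are scored as successes, 44 is reached with 44 − k true successes:

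- k = 1: 43/62 = 69.4%
- k = 2: 42/62 = 67.7%
- k = 3: 41/62 = 66.1%

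The intended threshold is 44/62 = 71.0%.

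**4. Effect on the chance of passing at a true 60% rate.** Let m be the share of arm B that is rescued, fails again before month 27 and is scored as a success. The scored rate is 0.60 + m. The protocol gives no value for m, so every row after the first is an assumption.

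| m | Expected patients (62 × m) | P(X ≥ 44 given p = 0.60 + m) |
|---|---|---|
| 0 | 0 | 0.049 |
| 1% | 0.62 | 0.068 |
| 2% | 1.24 | 0.091 |
| 3% | 1.86 | 0.120 |
| 5% | 3.10 | 0.198 |

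**5. Building m from assumed components.** Let m = q × 0.9 × s, where q is the share with early clinical progression, 0.9 the share of those rescued, and s the share of the rescued who fail again before month 27.

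- q = 0.10, s = 0.10: m = 0.009, 62 × 0.009 = 0.56 patients, probability 0.066
- q = 0.20, s = 0.10: m = 0.018, 1.12 patients, probability 0.086
- q = 0.20, s = 0.20: m = 0.036, 2.23 patients, probability 0.141

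The last line needs both ranges at their maximum. Here s includes deaths, which the general definition already counts as failures, so these values overstate the effect of re-progression alone.

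**The case against.** A reader might infer that the protocol orders every rescued patient to be counted as a success, even one who later progresses or dies. The documents do not support that.

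- The restart sentences are exceptions to a PFS definition given just before them, and they concern progression that came before restart. Section 13.1 is clearer still: the waiver attaches to the symptomatic episode. No text waives a second progression.
- Being considered progression free does not cancel death as a separate PFS event. The MRD guard does not mention death either, yet nobody would read it as making a death after MRD restart a success. Silence on death in these sentences is therefore weak evidence.
- Sections 9.4 and 11.1 treat progression after restart as real progression.
- The affected patient needs a clinical progression, restart, response and second progression, all within 12 months. Arm B starts MRD negative in blood and marrow and is tested every three months for the first two years, so some restarts will be triggered by MRD and fall under the guarded rule.

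Most of this stands. It removes the death claim as a defect, makes small numbers likely, and means that the inflation arises only if the literal reading is adopted. It does not remove the conflict: the closing sentence of the endpoint paragraph states a sufficient condition for the landmark status, and the guard is present for one restart group and absent for the other.

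Nor can this safely be left to the SAP, which is not available here. Section 14.4.6 says that deviations from the stated analyses may affect only the exploratory analyses. The protocol's own event rule therefore needs to be right.

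**Conclusion.** The point holds as a conflict within the protocol on the primary endpoint. For restart after clinical progression, the literal rule in 14.4.1 could score a second IWCLL progression before month 27 as a success, while the general PFS definition and section 13.1 point to failure. Death needs confirmation only.

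The direction is certain if the literal rule is applied: it can only add successes. The size is not known. One affected patient is enough to turn a failed result of 43 into a pass. Because the exact alpha is already 0.049, an assumed 1% affected takes the false-positive probability above 5%, to 0.068, and 2% takes it to 0.091. These probabilities rest on the assumed shares and on the literal reading. The sample size and threshold are unaffected. The rule should be corrected, but the conflict does not undermine the design.

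**What to change.** State in 14.4.1, and repeat in 13.1, that:

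- the rescue rule disregards only the initial progression that led to restart; and
- for both restart groups, a later IWCLL progression (after the rescue response, or after an MRD-triggered restart) or death from any cause, occurring up to month 27 (12 months after randomization), counts as failure.

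The clause should be tied to events up to month 27, not to an interval running from the response to the landmark. Section 14.4.1 allows three months from restart, so a response can fall after month 27 and that interval would run backwards. Section 13.1, by contrast, requires the response "before or at 12 months after randomization will neither be considered as progression". The two time limits should be reconciled in the same edit.

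The cost is one clause in two sections. Progression and death are already collected, and n = 62 and the threshold of 44 stay as they are. The downside is that the observed rate may be slightly less favourable.
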